4.2 Secondary Effectiveness Endpoints

The secondary effectiveness endpoints for this study are:

- Freedom from durable loss of renal function at Day 14
- Freedom from durable loss of renal function at Day 90

Reference creatinine values, baseline AKI stage and percentage loss of eGFR at Days 14 and 90 will be determined through algorithmic determination (see details above). Percentage loss of eGFR determined algorithmically will be based on a comparison of eGFR at screening compared to an algorithmically determined reference creatinine value

- Resolution of organ dysfunction (organ resolution is defined as having a total mSOFA score of ≤ 1) at Day 14
- Resolution of specific organ dysfunction (defined as having an individual organ mSOFA score of ≤ 1) at Day 14
- Critical care and hospital stay parameters
 - Hospital length of stay
 - ICU length of stay
 - ICU-free days in 28 days
 - Days on ventilator
 - Ventilator free days in 28 days
 - Vasopressor days
 - Vasopressor free days in 28 days
 - Discharge status

- Patient survival at Days 14, 28 and 90.
- Presentation of Stages 1, 2, or 3 AKI (using the KDIGO criteria)
- **Stratifications involving Day 14 mSOFA \leq 1 vs Day 14 mSOFA \geq 2**
 - Compare critical care between Day 14 mSOFA \leq 1 vs Day 14 mSOFA \geq 2
 - Compare dose groups in those with Day 14 mSOFA \leq 1
 - Compare dose groups in those with Day 14 mSOFA \geq 2
- Among patients presenting with cardiovascular failure (shock), dose group predicting Day 14 mSOFA \leq 1
- Survival to Day 90 as a function of *freedom from durable loss of renal function at 28* (overall and by dose group)

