6.1 Inclusion Criteria

1. Age: 18 up to and including 85 years.
2. Has either suspected or confirmed diagnosis of abdominal infection with planned or completed surgical (laparotomy or laparoscopy) or interventional radiologic procedures within 24 hours of evaluation by medical personnel, or surgically confirmed NSTI, requiring treatment with parenteral antibiotics. Recommended surgical or interventional radiologic procedures for abdominal infection be performed with 12 hours of evaluation by medical personnel.

A. Abdominal Infection

- a. Suspected clinical diagnosis of abdominal infection as evaluated by the attending surgeon including any of the following clinical criteria
 - Abdominal pain and/or tenderness
 - Localized or diffuse abdominal wall rigidity
 - Mass
 - Ileus

AND

- Any of the following radiologic findings
 - Free air (Plain film, CT or MRI scans)
 - Intraabdominal abscess (ultrasound, CT or MRI scans)
 - Free peritoneal fluid (ultrasound, CT or MRI scans)

OR

- b. Confirmed diagnosis of abdominal infection by any of the of the following criteria
 - Perforation and/or necrotic bowel with surgical confirmation of peritonitis
 - Presence of intraabdominal abscess by surgical confirmation or

drainage of purulent fluid from interventional radiologic procedure

OR

B. Necrotizing Soft Tissue Infection

- Surgical confirmation of NSTI by attending surgeon (e.g., presence of necrotic tissue, thrombosed vessels in the subcutaneous tissue, lack of bleeding and “dishwater” (cloudy, thin, gray) fluid due to presumed bacterial infection (necrotizing cellulitis (most commonly group A strep), necrotizing fasciitis, necrotizing myositis and myonecrosis, NSTI of the perineum, bacterial synergistic gangrene, Clostridial gas gangrene) that may be supported by specific signs and symptoms (e.g., tense edema outside area of compromised skin, pain disproportionate to appearance, skin discoloration, ecchymosis, blisters/bullae, necrosis, crepitus, and or subcutaneous gas).
3. SOFA score ≥ 2 (in any one or combination of the 6 major components of the SOFA score), measured as close as possible to study drug administration (but before study drug is administered).
 4. Planned or current admission to an ICU or step down unit (or equivalent).

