10.2 Secondary Efficacy Measures

- Rates of the primary endpoint at Day 14 between the Reltecimod- and placebo-treated patients
- To compare time to the primary endpoint between the Reltecimod- and placebo-treated patients
- AKI-free days over 14 and 28 days
- Resolution of organ dysfunction (organ resolution is defined as having a total SOFA score of ≤1) at Day 14
- Resolution of specific organ dysfunction defined as having an individual organ SOFA score of ≤1 at Day 14
- Critical care and hospital stay parameters
 - Hospital length of stay

- ICU-free days in 28 days
- Ventilator days
- Ventilator free days in 28 days
- Vasopressor days
- Vasopressor free days in 28 days
- RRT free days (days alive and free of RRT) in 28 days
- Patient survival at Days 14 and 28
- Presence of Stages 1, 2 or 3 AKI (using the KDIGO criteria) in patients with abdominal sepsis or NSTI

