12.2 Secondary Effectiveness Endpoints

The secondary effectiveness endpoints for this study:

- Rates of the primary endpoint at Day 14 between the Reltecimod- and placebo-treated patients.
- To compare time to the primary endpoint between the Reltecimod- and placebo-treated patients over 14 days
- AKI-free days over 28 days
- Time to the primary endpoint
- Resolution of organ dysfunction (organ resolution is defined as having a total SOFA score of ≤ 1) at Day 14

- Resolution of specific organ dysfunction defined as having an individual organ SOFA score of ≤ 1 at Day 14
- Critical care and hospital stay parameters
 - Hospital length of stay
 - ICU length of stay
 - ICU-free days in 28 days
 - Ventilator days
 - Ventilator free days in 28 days
 - Vasopressor days
 - Vasopressor free days in 28 days
 - RRT free days (days alive and free of RRT) in 28 days
- Patient survival at Days 14 and 28
- Presence of Stages 1, 2 or 3 AKI (using the KDIGO criteria) in patients with abdominal sepsis or NSTI

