5.3 Secondary Endpoints

The same analysis as described above will be performed for freedom from durable loss of renal function at Days 14 and 90 and from improvement for freedom from durable loss of renal function as Days 14, 28, and 90.

Additional secondary endpoints include mSOFA over time, critical care and hospital stay parameters (ICU and ICU-free days, ventilator days and –free days, vasopressor days and –free days, and hospital length of stay (LOS)). Analyses for these endpoints will generally be descriptive, with emphasis on characterizing clinical effect sizes. Nominal p-values will be presented. Categorical outcomes will be described using counts and percentages with nominal p-values determined through chi-square or exact methods. Critical care and hospital stay endpoints will be described using non-parametric approaches including using concordance statistics to characterize clinical effect sizes and Wilcoxon rank sum tests to determine nominal statistical significance. Methods appropriate for time-to-event endpoints including survival and life-table methods will be used for time-to-recovery endpoints.

5.4 mSOFA

The Sequential Organ Failure Assessment score or SOFA was originally developed to track a patient's status during a stay in an intensive care unit (ICU)^{4,5}. Each of six organ systems are evaluated and assigned ordinal scores from 0 to 4. A total score is the sum of the component scores. For this study, the liver component is excluded from the sum score and the resulting sum score is referred to in this study as 'mSOFA'.

Several approaches will be taken to summarize changes over time and between treatment groups in the clinical scores as described below. Special handling of mSOFA scores includes the following:

1. If an individual organ score is missing but other scores for that day are non-missing, the organ systems that were not evaluated are assumed to be free of organ failure and given a value of zero when determining the sum score.
2. If all organ scores are missing for a specific day, the mSOFA total score from that day will be imputed using LOCF with the following exception, LOCF will not be performed after patient death.
3. When summarizing the individual organ scores apart from the mSOFA total scores, the same rules as above will apply.

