8.3 Secondary and Exploratory AKI Recovery Endpoints

Table 14.2.2.1 summarizes treatment group comparisons based on secondary AKI recovery endpoints in the mITT analysis set including:

- Freedom from durable loss of renal function at Day 14
- Freedom from durable loss of renal function at Day 90
- Improvement or freedom from durable loss at Day 14
- Improvement or freedom from durable loss at Day 28
- Improvement or freedom from durable loss at Day 90

Tables 14.2.2.2 and 14.2.2.3 repeat these comparisons in the AT and PP analysis sets, respectively.

8.4 mSOFA Scores

Table 14.2.4.1 summarizes observed modified total score, organ specific scores, and mSOFA total scores at Screening, Day 1, Day 3, Day 7, and Day 14.

Table 14.2.4.2 provides the same summary after application of last-value-carried forward (LOCF). LOCF was not applied after patient death.

Table 14.2.4.3 summarizes mSOFA at Screening and changes from Screening to Day 1, Day 7, and Day 14 for observed cases.

Table 14.2.4.4 provides the same summary after application of LOCF.

Table 14.2.4.5 summarizes the percentages of subjects with resolution of organ dysfunction (organ resolution is defined as having a total mSOFA score of ≤ 1) at day 14 and the resolution of specific organ dysfunction defined as having an individual organ SOFA score of ≤ 1 at Day 14.

8.5 Critical Care and Hospital Stay Parameters, to be Measured until Day 28

The following critical care and hospital stay parameters will be assessed.

- Hospital length of stay (days)
- ICU free days
- Days in ICU
- Days on ventilator
- Ventilator free days
- Vasopressors days
- Vasopressors free days
- Discharge status

Because of the expected skewness in the distributions of these parameters, non-parametric Wilcoxon rank sum tests will be used to assess the nominal statistical significance of treatment group differences in these parameters. Table 14.2.5.1 will provide summary statistics by treatment groups including N, mean, median, standard deviation, and minimum, and maximum values.

Table 14.2.5.2 summarizes hospital discharge status.

Table 14.2.5.3 summarizes hospital readmissions.

Table 14.2.5.4 will summarize critical care and hospital stay parameters over days 1 to 28 comparing by primary effectiveness status (success versus failure).

Table 14.2.5.5 will summarize critical care and hospital stay parameters over days 1 to 28 comparing subjects with Day 14 mSOFA ≤ 1 versus Day 14 mSOFA ≥ 2 .

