32	14.2.1.4	Site Variability in Primary Efficacy Endpoint in the mITT Analysis Set
33	14.2.2.1	Numbers and Percentages of Subjects Achieving Secondary Freedom from or Improvement in Durable Loss of Renal Function Endpoints at Days 14, 28, and 90 mITT Analysis Set
34	14.2.2.2	Numbers and Percentages of Subjects Achieving Secondary Freedom from or Improvement in Durable Loss of Renal Function Endpoints at Days 14, 28, and 90 AT (Safety) Analysis Set
36	14.2.2.3	Numbers and Percentages of Subjects Achieving Secondary Freedom from or Improvement in Durable Loss of Renal Function Endpoints at Days 14, 28, and 90 Per Protocol Analysis Set

		SOFA
37	14.2.4.1	Modified SOFA Total Score, Organ Specific Scores, and SOFA Total Score At Screening, Day 1, Day 3, Day 7, and Day 14 By Treatment Group Observed Cases mITT Analysis Set
38	14.2.4.2	Modified SOFA Total Score and Organ Specific Scores Over Time to Day 14 By Treatment Group Last Observation Carried Forward (LOCF) By Treatment Group mITT Analysis Set†
39	14.2.4.3	Modified SOFA Total Score, Organ Specific Scores, and SOFA Total Score At Screening and Changes from Screening to Day 1, Day 3, Day 7, and Day 14 By Treatment Group Observed Cases mITT Analysis Set†
40	14.2.4.4	Modified SOFA Total Score, Organ Specific Scores, and SOFA Total Score At Screening and Changes from Screening to Day 1, Day 3, Day 7, and Day 14 By Treatment Group Last Observation Carried Forward (LOCF) mITT Analysis Set†
41	14.2.4.5	Resolution of Organ Dysfunction to Days 14 Overall and by Individual Organ By Treatment Group mITT Analysis Set
42	14.2.4.6	Resolution of Organ Dysfunction to Days 14 Overall and by Individual Organ By Treatment Group mITT Analysis Set Among Subjects Presenting with Shock
43	14.2.4.7	Resolution of Organ Dysfunction to Days 14 Overall and by Individual Organ By Treatment Group PP Analysis Set
44	14.2.4.8	Resolution of Organ Dysfunction to Days 14 Overall and by Individual Organ By Treatment Group PP Analysis Set Among Subjects Presenting with Shock

Critical Care		
45	14.2.5.1	Critical Care and Hospital Stay Parameters Over Days 1 to 28 By Treatment Group mITT Analysis Set†
46	14.2.5.2	Hospital Discharge Status By Treatment Group mITT Analysis Set
47	14.2.5.3	Hospital Readmissions By Treatment Group mITT Analysis Set
48	14.2.5.4	Critical Care and Hospital Stay Parameters Over Days 1 to 28 By Primary Effectiveness Endpoint* Success vs. Failure mITT Analysis Set

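### The individual-organ resolution endpoint at Day 14 has no baseline-dysfunction condition, so organs that were unaffected at screening or not measured count as resolved

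*SAP*

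**What the plan says.** **Definition.** SAP 4.2 gives the endpoint as "Resolution of specific organ dysfunction (defined as having an individual organ mSOFA score of" 1 or less, at Day 14. SAP 8.4 uses the same rule for the results: "resolution of specific organ dysfunction defined as having an individual organ SOFA score of" 1 or less. Protocol 10.2 has "Resolution of specific organ dysfunction defined as having an individual organ SOFA score of" 1 or less, and protocol 12.2 repeats it. None of the four places mentions the organ's score at screening.

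**Denominator.** SAP Appendix 1 titles Table 14.2.4.5 "Resolution of Organ Dysfunction to Days 14 Overall and by Individual Organ By Treatment Group mITT Analysis Set". Table 14.2.4.7 is its per-protocol counterpart. Tables 14.2.4.6 and 14.2.4.8 repeat the two in patients presenting with shock.

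**Entry.** Protocol 6.1, criterion 3, asks for a SOFA score of 2 or more "in any one or combination of the 6 major components of the SOFA score". No particular non-renal organ has to be affected.

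**Unmeasured organs.** Under SAP 5.4, when other organ scores exist for the day, "the organ systems that were not evaluated are assumed to be free of organ failure and given a value of zero". The same section applies this rule to the individual organ scores.

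**Status.** SAP 5.3 calls the analyses of the SOFA and critical-care secondary endpoints generally descriptive, with emphasis on effect sizes and nominal p-values.

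**The concern.** The protocol's objective (5.2) is to compare resolution of organ dysfunction, for individual organs as well as for the total score. For the total score, entry itself supplies a baseline condition, or nearly so for mSOFA, which drops the liver. For a single organ there is none.

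Take a patient who enters with AKI and has a normal platelet count, GCS and oxygenation throughout. That patient is reported as having resolved coagulation, CNS and respiratory dysfunction. An organ that worsens from 0 to 1 also counts as resolved, and so does an organ nobody measured on Day 14.

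Two things are at stake. An effect confined to affected patients appears smaller than it is. And if chance puts more patients with a failing organ in one arm, that imbalance shows up as a treatment difference in resolution. The SAP says it wants to characterise effect sizes here, and the effect size is what the definition blurs.

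**Working it through.** **Plan's own figure.** Neither document states a rate, prevalence or power for this endpoint. The only sizing figure is for the primary endpoint, and I used it to check the power formula (pooled chi-square, no continuity correction):

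power = Φ{[Δ − z·√(2p̄(1−p̄)/n)] / √[(p₁(1−p₁) + p₀(1−p₀))/n]}

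With 75% v 50% and 60 per arm, one-sided 0.05 gives 0.8897 (SAP 2.1.2 states 0.890). One-sided 0.025 gives 0.8157 (protocol 12.5.2 states 0.816). Both reproduce.

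**Inputs for the illustrations (all assumptions).**
- f: share of patients with the organ at 2 or more at screening.
- s: probability that an unaffected patient scores 1 or less at Day 14.
- r: the same probability for an affected patient.

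The reported percentage in an arm is (1−f)·s + f·r.

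**Baseline imbalance, no drug effect.** s = 0.95 and r = 0.60 in both arms.
- 30% affected: 0.70×0.95 + 0.30×0.60 = 0.845.
- 40% affected: 0.60×0.95 + 0.40×0.60 = 0.810.
- Spurious difference: 3.5 points, that is 0.10×(0.95−0.60).

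**Dilution.** If s is equal in both arms, the all-patient difference is f×(r₁−r₀). With r = 0.80 v 0.60, the 20-point effect becomes 4, 6 or 10 points at f = 0.2, 0.3 or 0.5.

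**Power at the SAP's one-sided 0.05, 60 per arm.** The last column assumes the drug also prevents new dysfunction (s = 0.95 v 0.88).

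| f | All patients, s equal | Affected only (n per arm) | All patients, s = 0.95 v 0.88 |
|---|---|---|---|
| 0.2 | 92.0% v 88.0%: 18% | 28% (12) | 92.0% v 82.4%: 47% |
| 0.3 | 90.5% v 84.5%: 26% | 37% (18) | 90.5% v 79.6%: 51% |
| 0.5 | 87.5% v 77.5%: 42% | 52% (30) | 87.5% v 74.0%: 59% |

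At the protocol's one-sided 0.025 the three power columns are 11/17/30%, 18/25/39% and 35/39/47%. The ordering is the same. With s equal, restriction gains power; with a preventive effect of this size, the ranking reverses.

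**Share of resolved patients with nothing to resolve.** This is (1−f)s / [(1−f)s + f·r]. It exceeds one half only when f is below s/(s+r). For s from 0.85 to 1.0 and r from 0.5 to 0.7, that threshold lies between 0.55 and 0.67. Across f = 0.10 to 0.95, the share runs from about 95% down to about 6%.

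**Renal score.** Entry requires Stage 2 or 3 AKI, and the SAP's mITT set repeats this. Creatinine of 2.0 mg/dL or more, or urine below 500 mL/day, scores 2 or more (protocol Appendix C). Some Stage 2 patients can still score 1 or less. Doubling a reference below 1.0 mg/dL stays below 2.0. And 0.5 mL/kg/h at 45 to 80 kg ideal weight is 540 to 960 mL per 24 h, above the 500 mL cut. The kidney is nevertheless largely an affected organ.

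**The case against.** The definition is explicit and the same in both documents. Day 14 status in all treated patients is a legitimate quantity: it keeps the full denominator and picks up prevention of new dysfunction, which a restricted row would miss. That stands, and it is why the all-patient line should stay.

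The plan also gives the reader something on baseline. Tables 14.2.4.3 and 14.2.4.4 show organ scores at screening and changes from screening by arm, and the shock tables give an affected-only denominator for the cardiovascular score. SAP 5.7 plans stratified or logistic checks of imbalance but does not name this endpoint. SAP 5.6 lists a respiratory-failure subgroup, but only the renal tables are promised for it. These help interpretation. None corrects the resolution percentage for the respiratory, coagulation, CNS or renal scores.

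A reader might infer two stronger things. One is that the endpoint mostly counts patients with nothing to resolve. That is a claim about prevalence, and the documents give no baseline distribution of organ scores. The entry rule shows only that a non-renal organ can be at 0 or 1, not how often. The other is that restricting to affected patients always gains power. That holds in the illustration only while the drug has no effect in unaffected patients.

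**Conclusion.** The point holds as a defect of definition and labelling. What is called resolution is Day 14 status in the whole analysis set, with never-affected and unmeasured organs counted as successes.

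Its size cannot be fixed from the documents. Under the stated assumptions, a 10-point imbalance in organ involvement produces a 3.5-point false difference, and a 20-point effect in affected patients shrinks to between 4 and 10 points at prevalences of 20% to 50%. The problem is likely small for the renal score, already covered for the cardiovascular score by the shock tables, and undetermined for the others.

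The endpoint is secondary and descriptive and does not touch the primary test. It is still worth correcting before unblinding, because the plan as written does not answer its own objective on organ-level resolution.

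**What to change.** In Tables 14.2.4.5 and 14.2.4.7:
- Keep the all-patient line, but label it organ score ≤1 at Day 14.
- For each organ, add a resolution row limited to patients with a pre-dose screening score of 2 or more, counting those at 1 or less on Day 14.
- For each organ, add a new-dysfunction row: screening 1 or less, Day 14 score 2 or more.

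Align the wording in SAP 4.2 and 8.4. Say there how deaths before Day 14 count in the new rows, since SAP 5.11.3 stops LOCF at death without stating the denominator. A footnote with the number of Day 14 scores set to zero because unmeasured would cover what the restriction does not reach.

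The cost is SAP wording and two rows per organ. Screening and Day 14 scores are already collected, and the affected subset is defined before dosing. The downside is smaller denominators (12 to 30 per arm at 20% to 50% prevalence, taking 60 per arm) and more rows on an endpoint with nominal p-values only.

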4.3 Exploratory Effectiveness Endpoints

The following are exploratory endpoints for this study:

- Improvement or freedom from durable loss at Day 14
- Improvement or freedom from durable loss at Day 28
- Improvement or freedom from durable loss at Day 90
- Incidence of chronic kidney disease (CKD) at Day 90 as determined by detection of albuminuria and estimated glomerular filtration rate (eGFR) using CKD-EPI equation
- Urinary albumin/creatinine ratio will be summarized for measurements made at Screening, Day 1, Day 3, Day 7, Day 14, Day 29 and Month 3. The measure is used to assess kidney injury and is a marker of CKD
- CRP will be summarized for measurements made at Screening, Day 7, Day 14, and Day 29, and for changes from Screening to Day 7, Day 14, and Day 29.
- Evaluation of RRT use (i.e., type of RRT)

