5.3 Exploratory Objectives

- To compare the primary endpoint at Day 90 between the Reltecimod- and placebo-treated patients
- To compare the rates of improvement in durable loss of renal function (defined as alive, free of dialysis, and improvement leading to a lower AKI stage but no better than Stage 1 AKI) at Days 14, 28, and 90, between the Reltecimod- and placebo-treated patients
- To compare the distributions of acute kidney disease (AKD) stages (AKD 0, 1, 2, 3, and 3F) at Days 14 and 28 between the Reltecimod- and placebo-treated patients
- To conduct an exploratory evaluation of the incidence of CKD at Day 90
- To conduct an exploratory evaluation of survival status at Day 90 in the Reltecimod- and placebo-treated patients
- To conduct an exploratory evaluation of the primary endpoint by baseline pathogen
- To conduct an exploratory evaluation of RRT use (i.e., type of RRT)
- To evaluate the immunogenicity of Reltecimod
- To conduct an exploratory evaluation of plasma and urinary biomarkers in patients with AKI
- To conduct an exploratory evaluation of blood leukocyte transcriptome (RNA expression) profiling in patients with SA-AKI and compare genomic profile in patients treated with Reltecimod versus placebo
- To define potential surrogate biomarkers (systemic) that exhibit change from

baseline due to treatment with Reltecimod

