6.2 Exclusion Criteria

1. Has known prior history of CKD with a documented eGFR < 30 mL/min by a commonly used formula such as MDRD or Chronic Kidney Disease Epidemiology Collaboration (CKD-EPI), or known GFR < 30 mL/min.
 - a. Exception: Patients with history of CKD but no available prior eGFR who have documented normal kidney size on ultrasound or computed tomography (normal size defined above) evaluation (performed within 90 days of screening) will be eligible
2. Patients receiving RRT for chronic kidney disease: either hemodialysis, peritoneal dialysis, hemofiltration such as Continuous Veno-Venous Hemofiltration (CVVH) or hemodiafiltration.
3. Previously diagnosed with documented AKI in the last 30 days.
4. Documented primary glomerular disease or toxic tubulo-interstitial nephritis or other underlying renal diseases significantly effecting renal function (e.g., renal amyloidosis, polycystic kidney disease, renal cancer, renal abscess) at the time of AKI diagnosis.

5. Patients with overt peripheral vascular disease in the involved NSTI area - associated with ischemic wounds/ulcers or gangrene, and/or other significant symptoms of inadequate vascular supply or where limb amputation is considered likely within 7 days due to the peripheral vascular disease.
6. Diabetic patients with peripheral vascular disease who present with below the ankle NSTI.
7. Current condition of
 - (a) Inability to maintain a mean arterial pressure > 50 mmHg and/or systolic blood pressure > 70 mmHg for at least 1 hour prior to dosing despite the presence of vasopressors and IV fluids, or
 - (b) a patient with respiratory failure such that an SaO₂ of 80% for at least 1 hour prior to dosing cannot be achieved, or
 - (c) a patient with refractory coagulopathy (INR >5) or thrombocytopenia (platelet count <20,000) that does not partially correct for at least 1 hour prior to dosing with administration of appropriate factors or blood products
8. Severe neurological impairment due to cerebrovascular accident or cardiac arrest.
9. Recent cerebrovascular accident in the last 3 months.
10. Patients with cardiac arrest requiring cardiopulmonary resuscitation within the past 30 days.
11. Patient is not expected to survive throughout 28 days of study due to underlying medical condition, such as poorly controlled neoplasm (e.g. Stage III or IV cancer).

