9.3 Urinary Albumin/Creatine Ratio

Table 14.3.4.1 summarizes urinary albumin/creatinine ratio at Screening, Day 1, Day 3, Day 7, Day 14, Day 29 and Month 3 and changes in albumin/creatinine ratio. The measure is used to assess kidney injury and is a marker of CKD.

9.4 Incidence of Chronic Kidney Disease (CKD) at Day 90

Table 14.3.4.2 summarizes the incidence of chronic kidney disease (CKD) at Day 90 in the As Treated (Safety) Analysis Set by treatment group. The definitions provided in [Appendix 8](#) will be used.

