16.2 Immunosuppressant Medications

- Corticosteroids
 - Prednisone >40 mg/day
 - Hydrocortisone 160 mg/day
 - Methylprednisolone >32 mg
 - Dexamethasone >6 mg
 - Cortisone >200 mg
 - Betamethasone >4.8 mg

- Methotrexate
- Leflunomide (Arava) / Teriflunomide (Aubagio)
- Cyclophosphamide (Cytosan)
- Cyclosporine A
- FK506 (Tacrolimus)
- Azathioprine
- Mycophenolate Mofetil (MMF) (CellCept)
- Sirolimus (Rapamycin, Rapamune)
- Everolimus (Certican)
- Temsirolimus (Torisel)
- Gusperimus
- Thalidomide
- Antitumor Necrosis Factor (TNF) Agents
 - Entanercept (Enbrel)
 - Afelimomab (Fab 2)
 - Infliximab (Remicade)
 - Certolizumab (Cimzia)
 - Golimumab (Simponi)
- Interleukin-1 Receptor Antagonist (IL-1RA)
 - Kineret
- CTLA-4 Fusion Protein
 - Abatacept (Orencia)
 - Alefacept (Amevive)
 - Belatacept (Nulojix)
- Anti-CD20
 - Rituximab (Rituxan/MabThera)
 - Obintuzumab (Gazyva)
 - Ocrelizumab (Ocrevus)
 - Ofatumumab (Arzerra)
- Anti-CD52
 - Alemtuzumab (Campath)
- Anti-IL2

- Daclizumab (Anti-Tac, Zenapax)
 - Basiliximab (Simulect)
- Anti-IL6
 - Tocilizumab (Actemra/RoActemra)
- Anti-BAFF (B-cell activating factor)
 - Belimumab
- Integrin Inhibitor
 - Natalizumab (Tysarbi)
- Anti-CTLA 4
 - Ipilimumab
- Other Interleukins
 - Aldesleukin (Proleukin)
 - Canakinumab (ilaris)
 - Oprelvekin (Neumega)
- Anti-PDL1
 - Avelumab (Bavencio)
- Other Selective Immunosuppressants
 - Muromonab or OKT-3
 - Efalizumab (Raptiva): Anti-CD11a
 - Fingolimod (Gilenya): Sphingosine 1-phosphate receptor modulator
 - Eculizumab (Soliris): Anti-complement protein C5
 - Tofacitinib (Xeljanz): JAK-Stat Inhibitor
 - Apremilast (Otezla): PDE-4 Inhibitor
 - Vedolizumab (Entyvio): Integrin $\alpha 4\beta 7$

17 Appendix 8: CKD Definition and Classification

17.1 CKD Definition:

A patient is said to have chronic kidney disease (CKD) if they have abnormalities of kidney function or structure present for more than 3 months. The definition of CKD includes all individuals with markers of kidney damage (see below*) or those with an eGFR of less than 60 ml/min/1.73m² on at least 2 occasions 90 days apart (with or without markers of kidney damage).

*Markers of kidney disease may include: albuminuria (ACR > 3 mg/mmol), haematuria (or presumed or confirmed renal origin), electrolyte abnormalities due to tubular disorders, renal histological abnormalities, structural abnormalities detected by imaging (e.g. polycystic kidneys, reflux nephropathy) or a history of kidney transplantation.

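### The Day 90 CKD incidence has no CKD-free denominator, and its two-occasion eGFR rule can be met with a value taken during the acute kidney injury

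*SAP*

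**What the plan says.** The protocol's exploratory objective (Section 5.3) is "To conduct an exploratory evaluation of the incidence of CKD at Day 90". SAP Section 4.3 makes this "Incidence of chronic kidney disease (CKD) at Day 90 as determined by detection of albuminuria" together with eGFR by the CKD-EPI equation. SAP Section 9.4 states that the table "summarizes the incidence of chronic kidney disease (CKD) at Day 90 in the As Treated (Safety) Analysis Set by treatment group", using the definitions in Appendix 8.

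Appendix 8 (Section 17.1) describes what it means to have CKD: "abnormalities of kidney function or structure present for more than 3 months". It then admits anyone with a marker of kidney damage, including an albumin/creatinine ratio (ACR) above 3 mg/mmol, or anyone with eGFR below 60 "on at least 2 occasions 90 days apart". It does not say which eGFR measurements may serve as those occasions. It attaches no repeat requirement to the marker route.

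On entry, exclusion 1 in Protocol Section 6.2 reads "Has known prior history of CKD with a documented eGFR" below 30 mL/min. An exception admits patients with a CKD history and no earlier eGFR if kidney size is normal.

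**The concern.** An incidence needs a population free of the condition at the start. Here the denominator is everyone treated, and the case definition does not distinguish old disease from new. A patient whose eGFR was 45 before the illness and who returns to 45 has regained full prior function, yet is tabulated as an incident case.

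The two-occasion rule is meant to establish chronicity. If its first occasion can be a creatinine drawn during the Stage 2 or 3 AKI that qualified the patient, chronicity rests on a single later measurement.

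What is at stake is how the trial's CKD result is read. A by-arm table labelled incidence will be taken as showing whether the drug prevents new chronic disease.

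**Working it through.** The plan gives no rate, power or sample size for this endpoint, so there is no figure to reproduce. The check uses the visit schedule, the SAP's eGFR formula and an illustration with assumed rates.

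**1. Which scheduled creatinines can be 90 days before the final visit?** Creatinine is scheduled at screening, Days 1, 2, 3, 7 (±1), 10, 14, 21 and 29 (+3), then 3 to 21 days after Visit 9 (Visit 10), then the final visit (SAP Section 3.8; Protocol Section 7.3 and Appendix A). The final visit is Day 90 to 95 in the protocol but 3 months ±5 days in SAP Appendix 5, so Day 85 is included. Gap = final day minus earlier day.

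| Earlier value | Final Day 85 | Day 90 | Day 95 |
|---|---|---|---|
| Screening, 48 h before dosing (1 − 2 = −1) | 86 | 91 | 96 |
| Day 1 | 84 | 89 | 94 |
| Day 2 | 83 | 88 | 93 |
| Day 3 | 82 | 87 | 92 |
| Day 6 (earliest for the Day 7 visit) | 79 | 84 | 89 |
| Day 29 | 56 | 61 | 66 |
| Visit 10, earliest (29 + 3 = 32) | 53 | 58 | 63 |
| Visit 10, latest (32 + 21 = 53) | 32 | 37 | 42 |

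Only screening to Day 3 can reach 90 days, and those values belong to the acute phase. From Day 6 onward the longest gap is 89. At a Day 85 visit no scheduled pair qualifies.

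**2. Is an acute-phase eGFR below 60?** The endpoint uses CKD-EPI, whose coefficients are not in the documents. As a stated assumption, the MDRD form in SAP Section 3.10.2 (creatinine exponent −1.154) stands in.

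- Two-fold creatinine: 2^−1.154 = 0.449. A reference eGFR of 75 becomes 33.7. The result is below 60 for any reference below 60/0.4494 ≈ 133.
- Three-fold creatinine: 3^−1.154 = 0.281. A reference of 75 becomes 21.1. The result is below 60 for any reference below about 213.
- For patients without a reference, the Appendix F entry creatinines, taken at the youngest age in each band, give eGFR of about 30 to 34.

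So most patients who qualify by creatinine have an acute value below 60. If the dates allow, one Day 90 value below 60 completes the pair.

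**3. What does prior CKD do to the comparison?** Let q be the share with prior CKD, equal in both arms and all counted at Day 90. Assume new-CKD rates of 35% and 20% among the rest. The tabulated rate is q + (1 − q) × new rate, so the difference is (1 − q) × 15 points.

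| q | Tabulated rates | Difference (points) |
|---|---|---|
| 0% | 35% vs 20% | 15 |
| 10% | 41.5% vs 28% | 13.5 |
| 20% | 48% vs 36% | 12 |
| 30% | 54.5% vs 44% | 10.5 |

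Neither q nor the new-CKD rates are in the documents.

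**4. Can prior CKD be read off the derived reference?** Not reliably. With no historical creatinine, SAP Section 3.10.1 back-calculates the reference from an eGFR of 75. Section 3.10.6 can replace a reference creatinine above 1.4 with that estimate. A measured value and the medical history are needed.

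**The case against.** Several points on the other side stand.

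- Appendix 8 opens with a duration of more than 3 months. A patient with normal values on Days 14, 21 and 29 does not plainly meet that because two distant values are low. A reader might infer that persistence is not required at all. The text does not support that. It is silent on which values count, and the operational rule does not look at the values in between.
- The calendar limits how often an AKI value can serve. Dosing follows AKI confirmation within 6 hours, so the qualifying creatinine will often fall on Day 1 or the day before, 89 or 90 days before a Day 90 visit. In a patient watched for 48 hours, the earliest screening value may precede the AKI. A pre-admission value could also be the first occasion, but if below 60 it points to pre-existing disease.
- Patients who enter on urine output alone may have a screening eGFR of 60 or more. Their share is unknown.
- Exclusion 1 is not the only filter. Exclusions 2 and 4 remove chronic renal replacement therapy, documented primary glomerular disease and other significant renal disease, so the prior-CKD pool is narrower than exclusion 1 alone suggests.
- The documents use the word incidence loosely. AKI stage incidence in Protocol Section 5.2 becomes presence in Section 12.2, so part of this is labelling.

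None of these supplies a CKD-free denominator or a rule on qualifying values.

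**Conclusion.** The point holds. As written, patients with prior CKD who are still below 60 or albuminuric at Day 90 are counted as incident, and the two-occasion rule can be met, for most creatinine-qualified patients, by an acute-phase value plus one Day 90 value.

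Two stronger conclusions are not supported. A reader might infer that every patient with prior eGFR of 30 to 59 is counted; the documents do not show that for those who die before Day 90. A reader might also infer that a drug effect on new CKD is hidden. Under randomization it is diluted, in the illustration from 15 points to between 10.5 and 13.5, although chance imbalance in prior CKD would also enter the comparison.

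The conclusion rests on MDRD standing in for CKD-EPI and, for the dilution only, on assumed rates. Its weight is modest: one exploratory table, with the primary test, alpha and sample size untouched.

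**What to change.** Amend SAP Sections 4.3 and 9.4 and Appendix 8 before unblinding:

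- Report Day 90 CKD prevalence for all patients, under that name.
- Report new CKD only among patients with a measured pre-illness reference eGFR of 60 or more and no CKD history. Show prior-CKD patients and those without a measured reference separately. Use one stated equation for reference and Day 90 eGFR.
- Bar screening and Day 1 to 3 values as a qualifying occasion.
- Require eGFR below 60 at Visit 9 or 10 and again at Day 90, or raised ACR at Day 29 and again at Day 90. Visit 10 collects creatinine only, so it cannot supply an ACR.
- State that these intervals fall short of 3 months. For a final visit on Day 90 to 95 they are 58 to 66 days from Visit 9 and 37 to 63 from Visit 10. The result should be called persistent reduced function or albuminuria at Day 90, not fully confirmed CKD. Full confirmation would need a further measurement after Day 90.
- Reconcile the final-visit window between protocol and SAP. Say whether the Day 90 carry-forward in SAP Section 5.11.2 applies here, since a carried value cannot be a second occasion.

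Creatinine, ACR and medical history are already collected, so the cost is wording and programming. The price is a smaller denominator for new CKD and a shorter confirmation interval.
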